#### 19.11. HANDLING OF MISSING DATA

For the primary analysis, only complete data will be used. Data will be considered “complete” if the subject had the event of interest at or prior to the time point for analysis and/or if the subject’s status is known at any time beyond the analysis window. Subjects without sufficient follow-up based on the lower end of the visit window will be excluded from the analysis (that is, subjects must have at least 28 days of follow-up for the 30 day endpoints, 6 months minus 30 days for the 6 month endpoints and 12 months minus 30 days for endpoints defined at 1 year). Thus, subjects without events but whom are known to be event free at a later visit will have their data imputed backward but not forward for the primary analysis.

As a sensitivity analysis, missing values for the primary endpoints will be replaced by regression imputations based on a multivariate logistic regression analysis of completed cases (those that have follow-up at the required time point or experienced the endpoint in question prior to final follow-up visit). Covariates to consider for inclusion in the logistic regression include but are not limited to: age, sex, history of hypertension, diabetes, previous peripheral vascular intervention, BMI, dissection location (mid popliteal (P2), distal popliteal (P3), tibioperoneal trunk, peroneal, anterior tibial, or posterior tibial), and baseline Rutherford class. Backward selection will be used to identify predictors. In the event there are no significant predictors in the logistic regression model at  $\alpha=0.1$ , a “hot deck” method will be employed where a random selection of the outcome from a group of completed cases with similar baseline characteristics will be used as the imputed value using simple random sampling with replacement. The baseline characteristics to be used for the hot deck method will include but are not limited to age ( $\neq$  median), sex, dissection location (mid popliteal (P2), distal popliteal (P3), tibioperoneal trunk, peroneal, anterior tibial, or posterior tibial), use of statin medication, current smoker status and baseline Rutherford class.

With either method of imputation, five complete datasets will be constructed. Each dataset will be analyzed separately and then combined in an overall analysis across the five complete datasets.

In addition, a tipping point analysis will be conducted whereby all subjects missing data for the endpoint of interest will be imputed as a failure one at a time until the point of tipping the analysis has been determined. That is, the tipping point analysis starts with the best case analysis (all missing subjects are a success) and continues until the worst case analysis is completed (all missing subjects are failures), by increasing the number of missing cases imputed as failures by one in each analysis. The goal of the tipping point analysis is to determine at what point the imputation of failures causes the statistical evaluation of the endpoint to lose statistical significance.

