### 7.3. CLINICAL STUDY DURATION & FOLLOW-UP

The follow-up duration for each enrolled subject is 36 months. Any subject who is enrolled but does not receive at least one Tack implant will be followed for 30 days and then exited from the study (see **Section 13.3.1**).

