#### 13.3.1. ENROLLMENT (INTENT-TO-TREAT)

A subject is defined as an intent-to-treat (ITT) and officially enrolled in the study once the Tack Endovascular System is advanced through the introducer sheath. Subjects in whom at

least one Tack implant is not placed, will be exited after 30 days. Subjects in whom at least one Tack implant is placed will be followed for 36 months.

In addition, the per-protocol (PP) population will be defined as ITT subjects with evaluable data that have met the definition for device success, excluding subjects with major deviations such as:

- A major inclusion/exclusion criterion deviation; or
- A major procedural deviation

The criteria for deviations meeting the classification of “major” will be defined by an independent designee before study endpoint data is available for statistical analysis.

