### 19.2. ANALYSIS POPULATIONS

Subjects with BTK PAD who receive PTA in the Mid/Distal Popliteal, Tibial, and Peroneal Arteries and have a resulting dissection(s) that an Investigator would otherwise treat by means such as additional angioplasty with extended inflation time or stenting, are eligible for enrollment. To be enrolled, subjects must meet all inclusion criteria and not meet any of the exclusion criteria

The intent to treat (ITT) population will consist of all subjects who had the Tack Endovascular System advanced through the introducer sheath. ITT subjects are included in both primary and secondary endpoint analyses.

The PP population will be the subset of the ITT population that have met the definition of device success and have not had any major protocol deviations. Major protocol deviations include:

- A major inclusion/exclusion criterion violation; or
- A major procedural deviation

The criteria for deviations meeting the classification of “major” will be defined by an independent designee before study endpoint data is available for statistical analysis.

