and a one-sided Type I error rate of 2.5%, a sample size of 171 subjects provides 90% power to demonstrate that the observed 30-day MALE+POD rate is below the performance goal of 12%.

Since the required sample size for the primary efficacy endpoint (186), is larger than the required sample size for the primary safety endpoint (171), an effective sample size of 186 subjects meeting the ITT definition will be assumed. Assuming approximately 20% loss to follow-up, total enrollment will be  $186/0.80$  or 232 subjects.

The secondary endpoint of primary patency of the tacked segment of the treated lesion at 6 months will also be formally tested against a performance goal of 64%. The performance goal of 64% was chosen as a result of a meta-analysis combining 13 papers that reported 6-month patency for standard PTA or from which the 6-month patency rate could be derived. These papers covered several patient populations, however all these populations are target populations for use of the Tack. A meta-analysis was performed on the results reported in these papers and the random effects estimate of 6-month patency was 63.5%. Therefore, 64% was chosen as the performance goal. Assuming an observed 6-month patency rate of 81% and a one-sided Type I error rate of 2.5%, the effective sample size given above for the primary efficacy endpoint of 175 would provide greater than 90% power to detect the difference between an observed 6-month patency of 81% and the performance goal of 64%.

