##### 19.8.2. PRIMARY EFFICACY

The primary efficacy endpoint of freedom from MALE at 6 months plus POD at 30 days will be analyzed using a one-sided, single group, Z-test comparing the observed proportion of subjects free of MALE and POD to the performance goal of 74%. The hypotheses are:

$$H_0 : P_{MALE\_6+POD} \leq 74\%$$

$$H_a : P_{MALE\_6+POD} > 74\%$$

where  $P_{\text{MALE}_{6+\text{POD}}}$  is the proportion of subjects free of MALE at 6 months + POD at 30 days. The p-value associated with the standard Z-test will be provided along with a one-sided 97.5% lower confidence bound on the point estimate observed. All subjects that meet the ITT definition are included in this analysis.

The Z-test that will be used for analysis is the continuity corrected Z under the estimated  $P_{\text{MALE}_{6+\text{POD}}}$ . That is:

$$Z = \frac{\hat{p} - P_0 + c}{\sqrt{\hat{p}(1 - \hat{p})/n}},$$

where  $\hat{p}$  is the estimate of  $P_{\text{MALE}_{6+\text{POD}}}$ ,  $P_0$  is the performance goal of 74% under the null hypothesis, and

$$c = \begin{cases} -\frac{1}{2n} & \text{if } \hat{p} > P_0 \\ \frac{1}{2n} & \text{if } \hat{p} < P_0 \\ 0 & \text{if } |\hat{p} - P_0| < \frac{1}{2n}. \end{cases}$$

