#### 19.12. STUDY SUCCESS DEFINITION

The trial will be considered a success if both the primary safety and primary efficacy endpoints are met.

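### ITT subjects who receive no Tack can enter the 6-month efficacy test only as failures, contrary to the all-ITT wording, and 186/0.80 holds 90% power only if loss leaves the analysed rate at 84%

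*Combined protocol and SAP*

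**What the plan says.** ITT status requires only that the device has been advanced through the introducer sheath; no implant is needed (sections 13.3.1 and 19.2). Section 19.2 states: "ITT subjects are included in both primary and secondary endpoint analyses". Section 19.8.2 repeats this for primary efficacy: "All subjects that meet the ITT definition are included in this analysis".

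Follow-up is shorter for ITT subjects without an implant. Section 7.3 says: "Any subject who is enrolled but does not receive at least one Tack implant will be followed for 30 days and then exited". Section 13.3.1 agrees: "least one Tack implant is not placed, will be exited after 30 days".

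Section 19.11 limits the primary analysis to complete data. A subject with the event at or before the time point is complete. An event-free subject must reach the lower end of the visit window, otherwise: "Subjects without sufficient follow-up based on the lower end of the visit window will be excluded from the analysis". For 6-month endpoints that limit is 6 months minus 30 days, about day 150. A subject known to be event-free at a later visit is filled in backward. Multiple imputation and a tipping-point analysis follow as sensitivity analyses; for the latter, "the tipping point analysis starts with the best case analysis" and it moves to the worst case.

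Section 19.6 sets 186 evaluable subjects (74% goal, 84% assumed, one-sided 0.025, 90% power) and then enrolment: "Assuming approximately 20% loss to follow-up, total enrollment will be" 186/0.80, or 232. Section 19.12 states: "The trial will be considered a success if both the primary safety and primary efficacy endpoints are met".

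**The concern.** The completeness rule treats the two outcomes differently. A failure counts however short the follow-up; a success counts only from about day 150. For a no-Tack subject exited by design at day 30, only one outcome is possible in the 6-month test. Contact effort cannot change that, because section 15.7 deals with missed visits. The analysis that decides the trial is therefore not the all-ITT analysis that the plan describes.

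The same rule affects the loss allowance. Dividing 186 by 0.80 assumes that loss removes failures and successes in proportion. Under 19.11, lost subjects' failures before exit stay in and their event-free outcomes go out, so the analysed rate falls below the true rate. At stake are an understated efficacy rate, a missed success, and a primary result whose population is unclear.

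The text also does not settle what happens to a subject who dies without MALE after the POD period and before about day 150. Such a subject has no endpoint event and insufficient follow-up, and so may be excluded.

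**Working it through.** **Plan's own figure.** The inputs from 19.6 are p0 = 0.74, p1 = 0.84, one-sided alpha 0.025 and 90% power.
- n = [(1.96·√(0.74·0.26) + 1.2816·√(0.84·0.16)) / 0.10]² = 176.8.
- With continuity correction: (176.8/4)·(1 + √(1 + 2/(176.8·0.10)))² = 186.6, against 186 stated.
- 186/0.80 = 232.5, against 232 stated. The plan's figures reproduce.

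**Which subjects the rule admits at 6 months**

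| Subject | Failure before exit | Event-free at exit |
|---|---|---|
| Tack placed, followed past about day 150 | counted | counted |
| Tack placed, lost before about day 150 | counted | excluded |
| No Tack, exited at day 30 | counted | excluded |

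**Method for power.** 232 are enrolled and the number of complete subjects is binomial. The test is the continuity-corrected Z of 19.8.2 (variance at the estimated rate) with its exact binomial rejection region at 1.96. The true ITT rate is 84% and loss is unrelated to outcome. Cumulative failure is assumed linear from 0 to 5% by day 30 (the 5% is 19.6's safety assumption), then linear to 16% by day 180. Exit times are assumed uniform within each window.

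**No-Tack exits alone** (3/35, feasibility study, section 4.2; 232·3/35 ≈ 20 subjects)
- Successes: 0.84·32/35 = 0.7680.
- Failures: 0.16·32/35 + 0.05·3/35 = 0.1506.
- Analysed rate: 0.7680/0.9186 = 83.6%. Power: 93.7%.

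**20% loss.** The 80% not lost contribute 0.672 successes and 0.128 failures.
- Loss over days 30-150: mean failure before exit is 0.05 + 0.11·60/150 = 0.094. Failures are 0.128 + 0.2·0.094 = 0.1468, and the rate is 0.672/0.8188 = 82.1%. Power: 77.7%.
- Loss over days 0-150: mean failure before exit is 0.2·0.025 + 0.8·0.094 = 0.0802. Failures are 0.1440, and the rate is 0.672/0.8160 = 82.3%. Power: 80.5%.
- Loss over days 0-180: mean failure before exit is (1/6)·0.025 + (5/6)·0.105 = 0.0917, so failures are 0.1463. One sixth of exits fall after day 150 and count as complete, which adds 0.2·(1/6)·0.851 = 0.0284 successes. The rate is 0.7004/0.8467 = 82.7%. Power: 85.3%.
- Outcome-neutral loss (analysed rate stays 84%): power 92.6%. This exceeds 90% because the Z of 19.8.2 is more powerful than the formula behind 186 (exact power 93.6% at n = 186).

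**If the 20% includes no-Tack exits.** 3/35 no-Tack plus 12.5% of the 32/35 with a Tack is 3/35 + 4/35 = 20%. Power over the same three windows is 81.5% to 85.5%.

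**Direction.** At a true rate of 74% and 20% random loss, the chance of success is 2.8% if no lost subject's failure is seen before exit, and 0.4% if half of them are. The rule is conservative under random loss.

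**The case against.** The all-ITT sentences can be read as naming the eligible set, with 19.11 saying how missing outcomes are handled. That is a fair reading for subjects lost by chance. It does not rescue subjects whose 6-month status the protocol itself declines to collect.

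The plan brings excluded subjects back through imputation and a full best-to-worst-case tipping point. This stands, and the dependence on missing outcomes will be visible. But success rests on the primary test. The imputation model is also fitted to completed cases, among which every no-Tack subject is a failure by construction.

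Twenty percent is an allowance, not a forecast. Section 15.7 requires repeated contact and delays exit for loss to follow-up, and backward filling recovers missed visits. This stands too: actual loss may be smaller.

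Section 19.6 calls 84% the observed rate. If that means the rate among analysed subjects, the neutral figure of about 93% applies and 232 is enough. The documents do not exclude this reading, so the power shortfall is conditional.

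A reader might go further in three ways that the documents do not support:
- **That the rule makes a false success easier.** Under random loss it does the opposite. Upward bias would need excluded subjects to do clearly worse after exit. The feasibility report attributes the three failed placements to tortuous anatomy and/or torque transmission in the catheter and does not show worse later outcomes.
- **That no-Tack exits cause the power shortfall.** Alone they leave about 94%; the shortfall needs ordinary loss among subjects with a Tack.
- **That later deaths without MALE are definitely dropped, or that Kaplan-Meier must replace the primary test.** The text leaves the first open, and the second is a trade-off.

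**Conclusion.** The inconsistency holds on the text alone: the 6-month primary test admits no-Tack ITT subjects only as failures, while 19.2 and 19.8.2 say ITT subjects are included. It concerns about 20 of 232 subjects if the feasibility proportion carries over. The 30-day safety endpoint is not affected in this way, since these subjects are followed for 30 days and the rule asks for 28.

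The power point is conditional. With 84% as the true all-ITT rate, 5% failing by day 30, uniform timing and outcome-independent loss of 20%, power falls short of 90% by about 5 to 12 percentage points. With 84% as the complete-case rate there is no shortfall. The harm is mainly the sponsor's risk of a missed success, together with an understated rate and an unclear population. The point should be settled before endpoint data are analysed.

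**What to change.** 1. Reconcile 19.2 and 19.8.2 with 7.3, 13.3.1 and 19.11. Either obtain 6-month MALE and vital status for no-Tack ITT subjects by phone or chart and count them in the primary test, or state that the 6-month primary efficacy analysis covers subjects with at least one Tack and apply that to failures and event-free subjects alike.
2. State how deaths without MALE after the POD period are handled.
3. State whether the 20% allowance includes no-Tack exits and whether 84% is the all-ITT or the complete-case rate, and restate power under the 19.11 rule. For scale: if the 20% includes 3/35 no-Tack exits and their status is collected, the existing test has about 89% to 92% power under the same assumptions.
4. Optionally, add a Kaplan-Meier estimate of the primary efficacy endpoint with its one-sided 97.5% lower bound as a sensitivity analysis, but only with item 1 in place. Otherwise it gives no-Tack subjects the later hazard of subjects with a Tack.

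The cost is SAP wording plus either a short status contact for about 20 subjects, added by amendment, or a narrower stated population that says nothing about patients in whom no Tack could be placed. The restated power may be less favourable than 90%.

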**Table 6** below summarizes the estimates for primary patency by vessel and by patient. At the close of the 6 and 12 month visit windows, the primary patency per patient was 80.6% and 66.4%, respectively.

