### 19.8.3. SECONDARY EFFICACY ENDPOINTS

The secondary efficacy endpoint of 6-month patency will be estimated as the proportion of tacked segments of the lesion(s) that are still patent at 6 months. A one-sided lower 97.5% confidence bound will be calculated for this estimate using the standard normal approximation. This lower bound will be compared to the performance goal of 64%. The hypotheses being tested are:

$$H_0 : P_{\text{Patency}_{6\text{month}}} \leq 64\%$$

$$H_a : P_{\text{Patency}_{6\text{month}}} > 64\%$$

where  $P_{\text{Patency}_{6\text{month}}}$  is the proportion of subjects whose tacked portion of the vessel is still patent 6 months post procedure. Patency will also be displayed using a Kaplan-Meier curve.

The secondary efficacy endpoint of target limb salvage at 6 months will be summarized using the Kaplan-Meier method to estimate freedom from above-ankle target limb amputation. The final 6-month estimate will be presented along with 95% confidence intervals. All subjects that meet the ITT definition are included in this analysis.

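### Section 19.11 lets a later scan fill a missed 6-month patency scan only as patent and gives no coding for a first occlusion at 12 months, so the tested patency estimate is biased upward unless most failures are seen early

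*Combined protocol and SAP*

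**What the plan says.** Section 19.11 uses complete data only. A subject is complete if the event occurred by the analysis time point, or if status is known at any time after the window. It adds that "subjects without events but whom are known to be event free at a later visit will have their data imputed backward but not forward". The minimum follow-up is set for the 30-day endpoints and then as "6 months minus 30 days for the 6 month endpoints and 12 months minus 30 days for endpoints defined at 1 year", so the rule is not confined to the two primary endpoints.

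Section 19.8.3 gives patency no missing-data rule of its own. It says that "6-month patency will be estimated as the proportion of tacked segments of the lesion(s) that are still patent at 6 months" and compares a one-sided 97.5% normal-approximation lower bound with the goal. Section 19.6 says that patency "will also be formally tested against a performance goal of 64" percent, and section 19.13 makes this the one formal test after the primaries. Failure is absence of flow in the tacked segment on duplex ultrasound, or on angiography where available (section 19.4). Table 8 schedules duplex at 30 days, 6 months and 12 months.

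**The concern.** The rule suits MALE, death and amputation. Those events have dates, so a subject who is event free later was event free at 6 months. Occlusion has no date; it is found only when someone looks. Take a subject with no occlusion seen earlier who misses the 6-month scan and has the 12-month one:

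- Flow at 12 months: patent at 6 months by backward imputation.
- No flow at 12 months: not event free later, and no event known by 6 months. No sentence makes this a 6-month failure. The subject is either dropped or, because status is known after the window and no event is recorded by 6 months, counted as event free.

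On either reading, later scans add successes without the matching failures. That raises the patency estimate and the chance of wrongly passing 64%.

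The case is foreseeable. Section 9.4 provides for scans done out of window or not at all. Section 15.7 keeps a subject in the study until two consecutive visits are missed and the 12-month window has passed, so someone absent at 6 months can return at 12. The planned sensitivity analyses do not expose the problem: regression imputation is for the primary endpoints, and the tipping-point analysis varies only subjects with missing data, whereas back-filled subjects count as complete.

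**Working it through.** **The plan's own figure.** Section 19.6 states: "Assuming an observed 6-month patency rate of 81% and a one-sided Type I error rate of 2.5" percent, "the effective sample size given above for the primary efficacy endpoint of 175 would provide greater than 90% power". The exact binomial probability that the normal-approximation lower bound exceeds 64% when true patency is 81% is 0.9996 at n = 175 and 0.9997 at n = 186, so the power statement reproduces. The same section also says "an effective sample size of 186 subjects meeting the ITT definition will be assumed"; the two sizes disagree, but patency power exceeds 90% with either.

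**Inputs.**
- q6, true 6-month patency: 0.64 (the goal), and 0.806 (earlier TOBA-BTK study).
- q12/q6: section 4.2 reports "At the close of the 6 and 12 month visit windows, the primary patency per patient was 80.6% and 66.4%, respectively", giving 0.664/0.806 = 0.824. That study's patency definition also included revascularization and amputation, so using its ratio here is an assumption.
- f, share missing the 6-month scan but having the 12-month scan: not in the documents; assumed 5-15%, missing at random.
- g, share of 6-month failures already seen at 30 days or on unscheduled imaging: not in the documents; assumed 0 or 30%.
- 186 subjects, one patency result each (a simplification).

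**Formula, with first occlusions at 12 months dropped:**

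estimate = [(1−f)·q6 + f·q12] / [(1−f) + f·(q12 + g·(1−q6))]

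At q6 = 0.64, q12 = 0.64 × 0.824 = 0.527. For g = 0:
- f = 5%: (0.608 + 0.0264)/(0.95 + 0.0264) = 0.650
- f = 10%: (0.576 + 0.0527)/(0.90 + 0.0527) = 0.660
- f = 15%: (0.544 + 0.0791)/(0.85 + 0.0791) = 0.671

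False-pass rates below are simulated (400,000 runs) with a one-sided 2.5% score test against 64%, so that the planned bound's own small excess is not mixed in.

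| f | g = 0: estimate | g = 0: false pass | g = 30%: estimate | g = 30%: false pass |
|---|---|---|---|---|
| 5% | 65.0% | 4.4% | 64.6% | 3.5% |
| 10% | 66.0% | 7.5% | 65.3% | 5.0% |
| 15% | 67.1% | 12.3% | 65.9% | 7.1% |

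At f = 2% and g = 0 the false-pass rate is about 3.0%. With the planned normal-approximation bound and g = 0, the rates at 5%, 10% and 15% are about 5.5%, 9.1% and 14.7%.

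**If a first 12-month occlusion is counted as event free at 6 months:** the estimate is (1−f)·q6 + f·[1 − g·(1−q6)]. With g = 0 this is 0.608 + 0.05 = 65.8% at f = 5% and 0.576 + 0.10 = 67.6% at f = 10%, with false-pass rates of about 7.8% and 18.4%.

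**Where the bias vanishes (dropped reading).** Setting the estimate equal to q6 gives g = q12/q6, so about 82% of failures would have to be seen early. Above that the bias reverses.

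**At 80.6%, g = 0:** the estimate becomes 81.3%, 81.9% and 82.6%, an inflation of 0.7, 1.3 and 2.0 points.

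**The case against.** The strongest reply has four parts.

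- A reader might infer that missed scans enter only as successes. They do not. Duplex is required at 30 days, and unscheduled target-limb imaging goes to the core laboratory. A no-flow finding on either before 6 months is an event by the time point and counts as a failure even if the 6-month scan is missed. This stands; it is why g is in the formula and why the g = 0 column is the upper end of the dropped reading.
- A reader might infer that the plan forbids carrying a 12-month occlusion back. It does not say so; it leaves the coding unstated. This also stands, but neither available reading makes that subject a 6-month failure, so the direction of the bias is unchanged.
- The share of missed scans is unsupported. The 20% in section 19.6 is loss to follow-up, not this group. The ±30-day window, the request to repeat non-diagnostic scans and the deviation rule should keep the share low. This is fair: at 2% the effect is small.
- Trial success rests on the two primary endpoints (section 19.12), for whose dated events the rule is sound. Patency is tested only after both pass, and at 81% it would pass anyway. This limits the severity but does not remove the upward bias in the reported estimate.

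**Conclusion.** The point holds in limited form. Among subjects with no earlier observed occlusion, section 19.11 lets a later scan fill a missed 6-month scan only as patent and leaves a first occlusion at 12 months uncoded. The formally tested patency estimate is biased upward unless about 82% or more of failures are seen early (at the earlier study's ratio, with 12-month occlusions dropped).

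At true patency of 64%, with 5-15% affected, the false-pass rate is about 4.4-12.3% with no early detection and 3.5-7.1% with 30% early detection. These figures rest on assumed shares, missingness at random and the earlier study's 12-to-6-month ratio. At 80.6% the estimate is inflated by up to 2.0 points and the decision is not at risk.

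The documents do not support a stronger conclusion, such as that trial success is compromised. This is a should-fix point.

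**What to change.** In section 19.11, limit backward imputation to dated clinical events: MALE, death, amputation and re-intervention. For every imaging-based patency endpoint, adopt one of these:

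- **(a)** Estimate 6-month patency with an interval-censored method that uses all scans, whether the next one shows flow or no flow, and name the method for the lower bound that is compared with 64%.
- **(b)** Score only scans or angiograms in the 6-month window, count an earlier no-flow as failure, and state that this is slightly conservative when scans are missed. With f = 10%, g = 30% and true 64%, the expected estimate is 0.576/(0.90 + 0.10 × 0.30 × 0.36) = 0.576/0.9108 = 63.2%.

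Do not simply carry both 12-month results back. That biases downward: at f = 10% the expected estimate is 0.576 + 0.0527 = 62.9% when truth is 64%.

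The cost is one SAP paragraph and a few more subjects missing for patency. At f = 10% and g = 30%, option (b) analyses about 186 × 0.9108 = 169 subjects, against about 179 under the present rule with occlusions dropped. Power at 81% against 64% stays near 100%.

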#### 19.6. SAMPLE SIZE

The sample size for the primary efficacy endpoint of freedom from MALE at 6 months plus POD at 30 days was calculated using a one-sided, single group, normal approximation test of a proportion (with continuity correction) against a performance goal. The performance goal for this endpoint is 74% developed based on the information reported in table VIIb and figure 2A of Conte (2009). From figure 2A, the estimated 6-month rate of freedom from MALE + POD in the infra-popliteal group is 80.5% with 95% confidence interval calculated to be (77%, 84%). Applying the recommended 3% margin to the lower bound of the confidence interval yields the 74% OPG. Assuming the observed freedom from MALE+POD is 84% and a one-sided Type I error rate of 0.025, a sample size of 186 subjects provides 90% power to detect this difference between observed freedom from MALE+POD and the performance goal of 74%.

The sample size for the primary safety endpoint of MALE+POD at 30 days was calculated using the exact binomial distribution. This is also a one-sided, single group test of a proportion against a performance goal. The performance goal for this endpoint was established at 12%. This performance goal was derived from the information reported in table VIIa of Conte (2009). In that table, MALE+POD was not reported, however MALE and 30-day death were reported separately. The sum of those two estimates (8.9%) was used for sample size calculation. Conte (2009) established performance goals for safety endpoints by constructing a 95% confidence interval and using the upper bound of that interval as the performance goal. With some algebraic manipulation, a similar 95% confidence interval was established for the 8.9% point estimate of 30day MALE+POD which resulted in an upper bound of 11.9%. Therefore 12% is used as the performance goal for this endpoint. Assuming an observed MALE+POD rate of 5%

 Joseph L. Mills, Sr, MD, [name], David G. Armstrong, DPM, MD, PhD, [name], [name], [name], MPH, and [name], on behalf of the Society for Vascular Surgery Lower Extremity Guidelines Committee, The Society for Vascular Surgery Lower Extremity Threatened Limb Classification System: Risk stratification based on Wound, Ischemia, and foot Infection (WIFI). J Vasc Surg. 2014; Volume 59, Issue 1, Pages 220–234.e2

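### The sensitivity imputation in Section 19.11 ignores event-free time before dropout, so on average it returns the complete-case rate instead of testing it

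*Combined protocol and SAP*

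**What the plan says.** Section 19.11 makes complete cases the primary analysis. A subject with an event at any time up to the time point counts as complete. An event-free subject counts only if followed to the lower end of the visit window, which is 6 months minus 30 days for efficacy. Others are excluded.

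The sensitivity analysis imputes missing primary endpoints from a logistic regression fitted to completed cases: "those that have follow-up at the required time point or experienced the endpoint in question prior to final follow-up visit". The named covariates are all baseline items, and the list is left open. On choosing among them the plan states: "Backward selection will be used to identify predictors". If nothing is significant at 0.1, a hot deck draws the outcome of a completed case with similar baseline characteristics, by "simple random sampling with replacement". Five data sets are built and combined.

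The same section then plans a tipping-point analysis that moves from all missing subjects as successes to all as failures. Kaplan-Meier appears in Section 19.8.3 for limb salvage and for the display of patency, but not for the primary efficacy endpoint.

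**The concern.** An early failure enters the completed set whenever it occurs. An event-free subject enters only by staying to the window. The completed set is therefore enriched for failures, and the imputation model is trained on that set.

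Nothing in Section 19.11 conditions on how long a missing subject was already event-free. Someone event-free to month 4 is imputed the same 6-month risk as someone lost on day 2. A sensitivity analysis built this way shares the selection of the analysis it is meant to check, so agreement between the two says little about the missing data.

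The covariate step adds a second weakness, because it asks a data-driven selection to work with few events per parameter.

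**Working it through.** **Plan's own figures.** Section 19.6 assumes 84% freedom against a 74% goal, one-sided 0.025, and states that "a sample size of 186 subjects provides 90% power to detect this difference".
- Uncorrected n = [(1.960√(0.74×0.26) + 1.282√(0.84×0.16))/0.10]² = 176.8. With continuity correction, (176.8/4)(1 + √(1 + 2/(176.8×0.10)))² = 186.6, which agrees with 186 within rounding.
- Safety at n = 171: reject at 12 or fewer events, exact one-sided level 0.0236, power 0.911 at a 5% rate. This agrees with the plan.
- Enrollment: 186/0.80 = 232.5, stated as 232.

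The plan gives no figure for the imputation step.

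**Inputs for the bias.** From the plan: 16% failure at 6 months (1 − 0.84), 20% loss and visits at 30 days and 6 months. The plan's 5% safety rate is taken as failure by day 30. Assumed: loss independent of outcome and uniform over 180 days; the other 11% of failures spread evenly over days 30–180; cut-off at day 150.

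**Case A, status known up to the day of loss.**
- The area under the failure curve is 0.75 + 15.75 = 16.5 days over 0–180, and 0.75 + 11.28 = 12.03 days over 0–150.
- Observed failures: 0.80×0.16 + 0.20×16.5/180 = 0.1463.
- Missing: 0.20×(150 − 12.03)/180 = 0.1533. Complete: 0.8467.
- Complete-case failure: 0.1463/0.8467 = 17.3%.
- Remaining risk in the missing: (0.16×150 − 12.03)/(150 − 12.03) = 8.7%.
- Planned imputation with no informative covariate: 0.1463 + 0.1533×0.1728 = 17.3%.
- Imputation conditional on event-free time: 0.1463 + 0.1533×0.0868 = 16.0%.

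**Case B, status known only at the visits.** One sixth of losses fall before day 30 (nothing known), four sixths between days 30 and 150 (day-30 status known), and one sixth after day 150 (treated as complete).
- Observed failures: 0.80×0.16 + 0.20×(4/6×0.05 + 1/6×0.16) = 0.140.
- Missing: 0.20×(1/6 + 4/6×0.95) = 0.160.
- Complete-case and imputed failure: 0.140/0.840 = 16.7%.
- Remaining risk in the missing: (1/6×0.16 + 4/6×0.11)/0.80 = 12.5%.

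**At 10% loss.** Case A: 0.1532/0.9234 = 16.6%. Case B: 0.150/0.920 = 16.3%. The bias is about 0.3–0.6 points.

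**Simulation of the planned procedure** (N = 232, 400 trials, covariates unrelated to outcome, constant hazard, no credit for the 30-day window). Complete-case and imputed freedom both averaged 82.1% against a true 84%; Kaplan-Meier gave 83.8%. Imputed minus complete-case averaged −0.01 points (SD 0.55, largest 2.5). The gap to the truth is wider than in cases A and B because window credit was omitted. The run is used only to show that the two estimates coincide on average.

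**Selection.** The named covariates are seven single-parameter terms plus six-level dissection location (5), which makes 12.
- Efficacy: 0.16×186 ≈ 30 failures; 30/12 = 2.5 per parameter.
- Safety: 0.05×186 = 9.3 to 0.05×232 = 11.6 events; 0.8–1.0 per parameter.
- With no true predictor, the chance of keeping at least one noise variable at 0.1 is roughly 1 − 0.9⁸ = 57% to 1 − 0.9¹² = 72%. Simulation gave 62–63%, so the hot deck would be reached only about 4 times in 10 even when nothing predicts.

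**The case against.** Several points on the other side stand.

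- **Other checks exist.** The tipping-point analysis rests on no model, covariate or donor, and it runs from best case to worst case. A reader might infer that the trial has no independent check on missing data; the same section shows otherwise. What the tipping point does not give is a plausible estimate.
- **Direction.** A reader might assume that the bias flatters the device. Under non-informative loss it lowers the event-free rate, so it is conservative.
- **Size.** It is tempting to say that imputation doubles the missing subjects' risk. That holds only in case A (17.3% against 8.7%). With status known only at visits the ratio is 16.7/12.5, about 1.3. The 20% loss is a planning allowance, and Section 19.11 back-fills from later visits.
- **Equality.** The imputed and complete-case rates agree in expectation only. A single trial can differ, and a covariate linked to both outcome and dropout would separate them.
- **Safety.** Few 30-day outcomes would be missing: under uniform loss, 0.20×28/180×232 ≈ 7 subjects. The poor event count there has little practical effect.
- **Hot deck.** Crossing the named variables gives 2×2×6×2×2×2 = 192 cells for about 186 donors, which might suggest that the method cannot run. The plan asks for similar donors, not exact matches. With margins from the earlier study's tables, and statin use and some location shares assumed, only about 10–15% of missing subjects would lack an exact match. The gap is an undefined similarity rule.

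None of this answers the central point: the model-based sensitivity analysis does not use event-free follow-up.

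**Conclusion.** The concern holds in limited form. For 6-month efficacy, the planned imputation repeats the complete-case selection and, on average, the complete-case answer. At 20% loss both overstate failure by about 0.7–1.3 points, against the device. The size depends on uniform, non-informative loss, on 5% failure by day 30, and on how closely status is tracked between visits. Informative loss could change the size and the direction.

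Backward selection is unstable rather than impossible. The documents do not support a reading that trial success is falsely protected or that the missing-data plan as a whole fails. This is a worthwhile improvement to a sensitivity analysis.

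One group needs separate thought. Sections 7.3 and 13.3.1 exit enrolled subjects with no Tack placed at 30 days, yet Section 19.8.2 includes all ITT subjects. Three of 35 in the earlier study had no Tack placed; at that rate, 3/35×232 ≈ 20 subjects would be missing at 6 months by design, for a reason tied to device failure. Conditioning on event-free time alone would give them a lower imputed risk than the plan does now.

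**What to change.** In Section 19.11, for the 6-month efficacy endpoint:

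1. Replace the sensitivity imputation with one conditional on being event-free at last contact, or add a Kaplan-Meier estimate with its lower 97.5% bound.
2. Use a small covariate set fixed in advance in place of backward selection. The hot-deck fallback is then not needed.
3. Treat deaths after day 30 explicitly as competing events, since Section 17.5 does not count them as endpoint events. A Kaplan-Meier estimate would then take its cumulative-incidence form.
4. Report subjects who exit at 30 days with no Tack placed separately, for example with a failure imputation.
5. Keep the tipping-point analysis as written.

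The cost is SAP wording and modest programming, with no change to visits or sample size. The new estimate will usually be slightly more favourable to the device than the planned one, so it should be shown beside the complete-case and tipping-point results and should not replace them.
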